9.2.1 Data entry

All data shall be entered in English. The eCRFs should always reflect the latest observations on the subjects participating in the study. Therefore, every effort should be made to complete the eCRFs within a reasonable time frame after the subject's visit. The subject's identity must always remain confidential, i.e. the name and address of the subjects must not be registered in the eCRFs or in the database. The Investigator must verify that all data entries in the eCRFs are accurate and correct. If some assessments are not done, or if certain information is not available, not applicable or unknown, the Investigator shall indicate this in the eCRF. The Investigator shall electronically sign off the study data. By signing, the Investigator takes responsibility for the accuracy, completeness, and legibility of the data reported to the Sponsor in the eCRF.

9.2.2 The query process

The monitor shall review the eCRFs and evaluate them for completeness and consistency. Each eCRF shall be compared with the respective source documents to ensure that there are no discrepancies between critical data. All entries, corrections, and alterations shall be made by the PI or his/her

Print date:

authorized designee. The monitor cannot enter data in the eCRFs. Once study data have been submitted to the central server via the eCRF, corrections to the data fields will be audit trailed, meaning that the reason for change, the name of the person who made the change, together with time and date will be logged. Roles and rights of the site personnel responsible for entering study data into the eCRF shall be determined in advance. If discrepant data is detected during review of the data, either by the Sponsor or by its representatives, the responsible data manager or monitor shall raise a query in the electronic data capture application. The query shall state the question or data to be changed and shall be resolved in the system by the PI or his/her authorized designee. The appropriate study site personnel shall answer the queries in the eCRF within a reasonable timeframe Answered queries will be audit trailed by the electronic data capture application meaning that the name of study site personnel, time, and date is logged. Answered queries will then be closed by the appropriate study personnel (i.e. data manager, site monitor, etc.)

9.2.3 User identification

eCRF records will be automatically appended with the identification of the creator, by means of their unique User ID. Specified records shall be electronically signed by the Investigator to document his/her review of the data and acknowledgement that the data are accurate. This will be facilitated by means of the Investigator's unique User ID and password; date and time stamps will be added automatically at time of electronic signature. If an entry in an eCRF requires change, the correction shall be made in accordance with the relevant software procedures.

9.2.4 Audit trail

All changes will be fully recorded in a protected audit trail and a reason for the change shall be stated. Once all data have been entered, verified, and validated, the database will be locked.

9.3 Source documents

Source documents are all documents used by the Investigator or hospital that relate to the subject's medical history, that verifies the existence of the subject, the inclusion and exclusion criteria, and all records covering the subject's participation in the study. They include laboratory notes, memoranda, material dispensing records, subject files, etc.

The Investigator is responsible for maintaining source documents. These shall be made available for inspection by the monitor at each monitoring visit. The Investigator must submit a completed eCRF for each subject for whom signed informed consent has been collected.

All supportive documentation submitted with the eCRF, such as laboratory or hospital records, shall be clearly identified with the CTN and subject number. Any personal information, including name, shall be removed or rendered illegible to preserve individual confidentiality.

9.4 Record keeping and access to source data

The Investigator/Institution shall permit study-related monitoring, audits, IRB review, and RA inspections and shall provide direct access to the source data/medical record including the identity of all participating subjects (sufficient information to link records, i.e. eCRF, medical records, original signed informed consent forms and detailed records of study product accountability). The records shall be retained by the Investigator as required by local legislation and international guidelines. Any transfer of responsibility for storage of the records shall be documented and the Sponsor shall be informed in writing.

The Sponsor shall verify that each subject has consented in writing to direct access to the original medical record/source data (by the use of written subject information and signed informed consent). The data recorded in the eCRFs will be checked for consistency with the source documents/medical record by the monitor during monitoring (source data verification; SDV). In order to be able to perform SDV, information about each subject's participation in the study has to be detailed in the medical record.

[figure not shown]

[figure not shown]
9.5 Document and data retention

All records pertaining to the conduct of the study, including signed eCRFs, informed consent forms, study product accountability records, source documents, and other study documentation must be retained for as long as is specified in the CTA. Measures shall be taken to prevent accidental or premature destruction of these documents (e.g. protection against damage and unauthorized access, preferably by storage in a fire-proof cabinet).

It is the Investigator's responsibility to inform the Sponsor in writing if the Investigator file is moved or if the responsibility for the documents is transferred to someone else.

10 Statistical Methods

10.6 Handling of missing data

All effectiveness endpoints will be evaluated based on observed cases.

[figure not shown]
10.7 Withdrawal and deviations

All withdrawn subjects will be listed individually, including at least subject number, date and reason for withdrawal, and last visit performed.

Subjects with CIP deviations will be listed individually, including subject number and observed deviation.

Deviations from the statistical plan will be documented in the statistical report.

Print date:

10.8 Sample size

11 Protection of personal data

All processing of personal data must be carried out in accordance with national legislation concerning the protection of personal data. The Institution and the Investigator are responsible for complying with all requirements pursuant to national legislation in which the Institution and the Investigator are located. The Sponsor will ensure that all requirements for data processing are fulfilled.

The Investigator understands that clinical studies conducted under an IDE are exempt from the study subject identifier confidentiality provisions of the Health Insurance Portability and Accountability Act of 1996 (HIPAA), and the study subject should be made aware of this exception in the informed consent. The Institution and Investigator are jointly responsible for providing sufficient information to all subjects to enable them to give their informed consent not only to the participation in the investigation, but also to the processing of Personal Data. Such information includes information regarding the purposes of the processing, the length of time during which Personal Data will be stored, the right of access to stored Personal Data and the right to correction or purging of incorrect or obsolete Personal Data. A subject may also withdraw his or her consent at any time.

A subject who withdraws his or her consent to the processing of Personal Data must be considered to have withdrawn from the investigation but the data collected until the consent was withdrawn may be used in the statistical analyses.

Authorized representatives from the Sponsor or a RA may visit the investigational site to perform audits/inspections, including source data verification, i.e., comparing data in the subjects' medical records and the eCRF. Data and information will be handled with strict confidentiality.

The study shall include collection and processing of personal data as specified in the Regulation (EU) 2016/679 (General Data Protection Regulation, GDPR) on the protection of individuals with regard to the processing of personal data. For the purposes of the study, Sponsor will be considered the data controller, and Institution and PI will both be considered data processors.

12 Quality Control and Quality Assurance

12.1 Quality control

On-site monitoring of the study will be arranged by the Sponsor according to GCP guidelines to verify that the rights and well-being of the subjects are protected, the reported data are accurate, complete, verifiable from source documents, and that the conduct of the study complies with the approved CIP, subsequent amendment(s), GCP and the applicable regulatory requirements.

Any CIP deviation shall be documented appropriately, verified, discussed, and collected by the monitor and appropriate actions will be taken. The PI is responsible for promptly reporting any deviations from the CIP that affects the rights, safety or well-being of the subject or the scientific integrity of the study, including those that occur under emergency circumstances, to the Sponsor as well as the IRB if required by national regulations. Deviations will be reviewed to determine the need to amend the CIP.

12.2 **Quality assurance**

The study site may be subject to quality assurance (QA) audit by the Sponsor as well as inspection by appropriate RA. It is important that the Investigator and other relevant study site personnel are available during the monitoring visits, possible audits, and inspections, and that sufficient time is devoted to the monitoring process.

Each participating member of the study site team shall provide a curriculum vitae (CV) or equivalent that demonstrates their qualifications to conduct the study.

It is the responsibility of the Investigator to ensure that all personnel involved in the study are fully informed of all relevant aspects of the study, including detailed knowledge of and training in all

procedures to be followed. All Investigators and other responsible persons shall be listed together with their function in the study on the signature and delegation log.

12.3 Changes to the Clinical Investigational Plan

The PI and other site personnel involved in the study must not implement any changes to the CIP without agreement with the Sponsor and prior review and documented approval from the IRB and RA, if applicable, except where necessary to eliminate an immediate hazard to the subjects. All changes to the final CIP must be documented in a dated and version-controlled written CIP amendment. However, administrative changes may be documented in the Sponsor file without requiring a CIP amendment. The Sponsor will assess if the changes require prior FDA approval, and inform the Investigator when such approval has been received.

13 Financing, Indemnification, and Insurance

The CTA outlines the compensation and payment terms of the study. The CTA must be signed before the first subject is screened in the study. If there are differences between the CTA and the CIP regarding certain rights and obligations, the CTA is the prevailing document. The Sponsor's obligations in this clinical study are covered by Galderma's global general liability program. An insurance certificate will be provided upon request. The Institution/Investigator is obligated to maintain insurance coverage for their obligations in the clinical study according to the CTA.

[figure not shown]

Suspension or Premature Termination

The Sponsor will suspend or terminate the study when so instructed by the IRB or RA, or if it is judged that the subjects are subjected to unreasonable risks, or for valid scientific or administrative reasons, or for business reasons.

The Sponsor may also decide to close a single study site due to unsatisfactory subject enrolment or noncompliance with the CIP, GCP, or applicable regulatory requirements.

In the event of premature termination, Q-Med AB will provide information on the handling of currently enrolled subjects who have not completed the study.

16 References

1.1 Background

This statistical analysis plan (SAP) describes the analysis variables and statistical procedures that will be used to analyze and report the results from the open label extension for Protocol 43USSA1705, named Protocol 43USSA1705ext (v3.0), dated 02 MAR 2020.

The SAP was written in accordance with the recommendations outlined in the International Conference on Harmonisation (ICH) E9 Guideline entitled “Guidance for Industry: Statistical Principles for Clinical Trials” and the ICH-E3 Guideline entitled “Guidance for Industry: Structure and Content of Clinical Study Reports”.

1.1.1 Study Design

This is a 48-week prospective, open-label follow-up study, with the aim to evaluate the long-term safety and effectiveness of treatment with Sculptra Aesthetic for correction of Nasolabial Fold (NLF) contour deficiencies. Participation will be limited to the five sites who participated in the 43USSA1705 study.

Eligible subjects in 43USSA1705 were treated with a single regimen of Sculptra Aesthetic [REDACTED]
[REDACTED]
[REDACTED]
[REDACTED]
[REDACTED]

[REDACTED]. Subjects will enter this extension study upon completion of the 43USSA1705 study and perform follow-up visits at [REDACTED] after baseline (i.e. Day1/first treatment session in the 43USSA1705 study).

1.1.2 Number of Subjects

Approximately 60 subjects will be recruited from five US sites [REDACTED]. Since this is an extension study, no sample size calculation is needed.

1.2 Study Objectives

1.2.1 Safety Objective

The objective is to evaluate the long-term safety of Sculptra Aesthetic as a single regimen [REDACTED]
[REDACTED]

1.2.2 Effectiveness Objective

The objective is to evaluate the long-term effectiveness of Sculptra Aesthetic as a single regimen for correction of NLF contour deficiencies [REDACTED]

1.3 Effectiveness Assessments

For all assessments, baseline will be defined as the observation that is closest to but prior to study treatment on Day 1 in study 43USSA1705. Likewise, change from baseline will be calculated as the value at a given time point minus the baseline value.

1.3.1 [REDACTED]

[REDACTED] is a validated photograph-based outcome instrument that is designed specifically for quantifying facial folds. Scoring of fold severity is based on visual assessment of the length and apparent depth of the wrinkle at a certain time-point. Scoring of the left and right nasolabial folds separately [REDACTED] will be based on visual live assessment by the Evaluator at defined time points, and not on a comparison to the baseline appearance.

[REDACTED] will be assessed at [REDACTED] after baseline.

[REDACTED]	[REDACTED]

1.3.2 [REDACTED]

The aesthetic improvement of the nasolabial folds will be assessed by the Investigator and the subject, independently of each other. [REDACTED]

[REDACTED] will be assessed by the Investigator and Subject at [REDACTED] after baseline. The following categorical scales will be used (Table 2).

[REDACTED]	[REDACTED]

[REDACTED] [REDACTED]

[REDACTED] is a patient-reported outcome instrument to evaluate the experience and outcomes of aesthetic facial procedures from the subject's perspective. [REDACTED]

[REDACTED].

1.3.4 [REDACTED]

[REDACTED] [REDACTED] ne.

1.4 Effectiveness Endpoints

- Change from baseline on both sides [REDACTED] as assessed by the Evaluator [REDACTED] after baseline.
- Responder rate using [REDACTED] at [REDACTED] after baseline.

[REDACTED]
[REDACTED].

- Responder rate using the [REDACTED] at [REDACTED] after baseline.

[REDACTED]
[REDACTED]

- [REDACTED] at [REDACTED] after baseline.
- [REDACTED] at [REDACTED] 2 and [REDACTED] after baseline.

1.5 Safety Assessments

The methods for collecting safety data are described in Section 7 of the Clinical Study Protocol.

1.6 Safety Endpoints

Safety endpoints include incidence, intensity, time to onset, and duration of adverse events collected throughout the study period.

2 Statistical Methods

2.1 General Methods

Any change made to the finalized SAP before database lock will result in a SAP amendment. Otherwise, the change will be documented in the Clinical Study Report (CSR).

Some of the analyses detailed here may be more explicit or in some aspects different from those stated in the protocol. In case of differences, this SAP supersedes the statistical sections in the protocol.

2.1.1 Programming Conventions

██████████ will have responsibility for performing analyses. All computations for statistical analyses will be performed using SAS® software, Version 9.4 or later. All SAS programs used in the production of statistical summary outputs will be validated with independent programming prior to finalization. In addition, all program outputs will be independently reviewed. The validation process will be used to confirm that all data manipulations and calculations were accurately done. Once validation is complete, a senior statistical reviewer will perform a final review of the documents to ensure the accuracy and consistency with this plan and consistency within tables. Upon completion of validation and quality review procedures, all documentation will be collected and filed by the project statistician or designee.

The electronic case report form (eCRF) data for all subjects will be provided in Standard Data Tabulation Model (SDTM) datasets. Analysis Data Model (ADaM) datasets will be developed from the SDTM datasets for use in table and figure production.

2.1.2 Reporting Conventions

The formats for the tables, listings, and figures described in this SAP will be provided in a companion document. Changes to the formats of these reports that are decided after the finalization of the SAP will not require an amendment. In addition, any additional supportive or exploratory analyses requested after SAP approval will not require amendment of the SAP. These additional analyses will be described in the CSR.

All study data from the eCRFs as well as derived variables will be provided in subject data listings. An indication of specific listings for each data type will not be indicated in the text of subsequent SAP sections. Data listings supplied as part of the CSR will be sorted by study center number concatenated with subject number, assessment dates, and/or time point.

The following conventions will be applied to all data presentations and analyses:

 GALDERMA	Title 43USSA1705ext SAP	Doc id
--	-----------------------------------	--------

Statistical Analysis Plan, Version 1.0 FINAL, 10 AUG 2020

- Quantitative variables will generally be summarized by the number of subjects, mean, standard deviation, median, minimum, and maximum. Unless otherwise specified, the minimum and maximum values will be displayed to the same number of decimal places as the raw data, the mean and median will be presented to one extra decimal place compared to the raw data, and the standard deviation will be displayed to two extra decimal places compared to the raw data
- Categorical variables will be summarized by the number and percentage of subjects (and number of events where appropriate) within each category. Unless otherwise specified, the percentage will be presented in parentheses to one decimal place. Frequency and percentage values of 0 will be presented as '0' rather than '0 (0)'.
- All summary tables will include the number of subjects.
- Date variables will be formatted as DDMMMYYYY for presentation.

2.1.3 Data Transformations

The [REDACTED] will be reported (Section 4).

2.2 Analysis Populations

Only one population will be defined: The Extension population. The Extension population includes all subjects entering the extension study. This would include all subjects who are signing the extension study informed consent.

2.3 Study Subjects

Demographic endpoints and subject characteristics will be summarized using descriptive statistics using the Observed Cases. There are no planned inferential statistical analyses of demographic endpoints or subject characteristics.

2.3.1 Subject Disposition

The number of subjects enrolled will be shown in total and by study center.

The disposition of subjects will be summarized, including numbers of subjects who were:

- Completed,
- Withdrawn (including primary reason for withdrawal).

These numbers will be summarized by study center. The number of subjects expected, completed, missed, and withdrawn will be summarized by scheduled visit.

- Expected = all subjects minus withdrawn subjects.
- Completed = subjects that showed up at that visit.
- Missed = expected subjects minus completed subjects.
- Withdrawn = all subjects who have withdrawn up to that visit.

All withdrawn subjects will be listed individually, by subject number, date and reason for withdrawal, and last visit performed.

Statistical Analysis Plan, Version 1.0 FINAL, 10 AUG 2020

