5.5 Withdrawal of subjects

Each subject shall be advised in the informed consent form that the subject has the right to withdraw from the study at any time, for any reason, without prejudice. Subjects may also be discontinued from Page 19 of 37

this study if the Investigator determines that it is in the subject's best interest to do so and may be withdrawn at the Investigator's discretion at any time.

The withdrawal criteria are:

The reason and date for withdrawal shall be documented in the eCRF. When possible, an explanatory comment shall be added to further explain the reason for withdrawal. If withdrawal of a subject occurs during a regular study visit, the eCRF for that specific visit shall be completed as far as possible.

If a subject is withdrawn from the study, all data collected until the time of withdrawal will be used in the analyses. Subjects who are withdrawn or discontinued from the study will not be replaced. For AEs still ongoing at the time of withdrawal, see section 7.2.6.

Study Products

No study products will be provided during this study.

6.1 **Investigational product**

No investigational product will be provided during this study.

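### Do the by-visit disposition formulas count a subject who withdraws at a visit twice, and so understate missed visits?

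*SAP*

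**What the plan says.** SAP section 2.3.1 sets out a by-visit attendance table: "The number of subjects expected, completed, missed, and withdrawn will be summarized by scheduled visit". It defines the four counts as follows.

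- The first count is net of those who have left: "Expected = all subjects minus withdrawn subjects".
- Attendance alone decides the second: "Completed = subjects that showed up at that visit".
- The third is a difference between the first two: "Missed = expected subjects minus completed subjects".
- The fourth accumulates over time: "Withdrawn = all subjects who have withdrawn up to that visit".

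The base is the single analysis population in SAP section 2.2: "The Extension population includes all subjects entering the extension study". Protocol section 5.5 says that subjects who leave are not replaced, so that base stays fixed. The same section covers a subject who leaves in the course of a scheduled visit: "If withdrawal of a subject occurs during a regular study visit, the eCRF for that specific visit shall be completed as far as possible".

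The SAP does not state whether the cumulative withdrawn count at a visit includes those who withdraw at that very visit.

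**The concern.** A subject who attends and withdraws on the same occasion meets the definition of completed, because he or she showed up. If the cumulative withdrawn count includes that visit, the subject also leaves the expected count. Missed is expected less completed, so it subtracts someone who was never in the expected total. Each such subject cancels one genuine absence, and when there are more of them than absences the count goes negative.

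The stake is how far a reader can trust the attendance table. Effectiveness is analysed on observed cases (SAP section 2.4.2), so visit attendance is useful context for judging how complete the data are. A negative count would stand out. A zero that hides two absences would look ordinary.

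**Working it through.** The plan gives no disposition figures, so there is none to reproduce. The check is an accounting identity worked under both readings.

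**Inputs**

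- N = 60, as an illustration, from SAP section 1.1.2: "Approximately 60 subjects will be recruited from five US sites".
- p = subjects who withdrew before the visit.
- a = subjects who attended the visit and withdrew at it.
- m = subjects still in the study who did not attend (the true number missed).

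The documents give no values for p, a or m. Those below are assumptions: p from 0 to 5, a from 0 to 3, m from 0 to 3.

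**Formulas**

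Completed is the same on either reading: C = N - p - m.

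- *Inclusive reading* (withdrawn at this visit counts now): W = p + a, E = N - p - a, so Missed = E - C = m - a.
- *Exclusive reading* (withdrawn at this visit counts from the next visit): W = p, E = N - p, so Missed = E - C = m.

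**Results with N = 60**

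| p | a | m | C | Inclusive: E, Missed | Exclusive: E, Missed |
|---|---|---|---|---|---|
| 2 | 0 | 3 | 55 | 58, 3 | 58, 3 |
| 2 | 1 | 3 | 55 | 57, 2 | 58, 3 |
| 2 | 1 | 0 | 58 | 57, -1 | 58, 0 |
| 0 | 2 | 2 | 58 | 58, 0 | 60, 2 |
| 5 | 3 | 1 | 54 | 52, -2 | 55, 1 |

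On the inclusive reading Missed is too low by exactly a, and is negative whenever a exceeds m. On the exclusive reading it equals m in every row. With a = 0 the two readings coincide.

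**Which reading does the text support?** The phrase *up to* a visit can mean before it or through it, and nothing in section 2.3.1 settles which. Two things favour the exclusive sense. A person who came to the visit was expected at it, so taking that person out of the expected count contradicts the label. And a subtraction intended to give a count of absences gives one in all cases only on that reading.

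**What else reports the same information?**

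- SAP section 2.4.2 provides for a summary of missing values that does not depend on the Missed row.
- SAP section 2.3.1 lists each withdrawn subject with when and why they left and the last visit they made, so every withdrawal at a visit can be identified and the row reconciled.
- SAP section 2.1.2 puts all eCRF data and derived variables in subject listings.
- The effectiveness summaries and exact intervals in SAP section 2.4.3 and the adverse event summaries in section 2.5.1 use neither Expected nor Missed.

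**The case for a change.** The best case for a change is that one text supports two programs with different output. The inclusive program is easy to write: withdrawal date on or before visit date. The SAP's validation by independent programming (section 2.1.1) would expose a disagreement between two programmers, but not an inclusive reading that both share. A row-total check would not help either, because C + Missed + W = N on both readings; for p = 2, a = 1, m = 3 the inclusive figures are 55 + 2 + 3 = 60. The exclusive reading also has a loose end: a subject who withdraws at the last scheduled visit has no later visit at which to appear as withdrawn, which might push a programmer towards the inclusive rule.

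Most of this is right as far as it goes. The boundary is undefined, the triggering case is one the protocol foresees, and an offset such as 0 reported against 2 true absences could pass unnoticed in the table itself. What does not stand is the step from there to an error in the plan. The double count follows from one of two available readings and is not a stated rule. The loose end at the last visit is covered by the overall disposition summary and the withdrawal listing in the same section. A negative count would be conspicuous at the senior statistical review in section 2.1.1, and an offset one can be traced through the listing. Writing the boundary into the SAP would spell out the exclusive reading and would alter no result.

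**Conclusion.** No change is needed. SAP section 2.3.1 leaves open whether a subject who withdraws at an attended visit is withdrawn at that visit or from the next. Counted from the next visit, the definitions are consistent and Missed is correct. Counted at that visit, Missed is low by the number of such subjects, which was 1 to 3 in the affected cases worked here. Those counts are assumptions, since the documents give no withdrawal figures.

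At worst, one descriptive row is off by a few in a study of about 60 subjects, with the means to correct it in the listings. No endpoint, responder rate, confidence interval or adverse event summary would move. The conclusion rests on the programmers treating someone who attended as expected, which is the ordinary sense of the word. If they did not, the effect would still be confined to that table.
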